11. MEASUREMENT OF EFFECT

Although response is not the primary endpoint of this trial, patients will be assessed for objective response by the standard criteria of modified IWG-2006 guidelines ([Appendix A1](#) and [Appendix A2](#)). Responses in AML patients will be assessed using IWG 2003 criteria ([Appendix A3](#)). In addition to a baseline bone marrow biopsy and scan, bone marrow biopsy will be performed at baseline, after cycles 2 and 4, and before each maintenance dose.

11.1 Definitions

Evaluable for toxicity. All patients will be evaluable for toxicity from the time of their first treatment with Entinostat in combination with Pembrolizumab (MK-3475)

Evaluable for objective response. Only those patients who have measurable disease present at baseline, have received at least one cycle of therapy, and have had their disease re-evaluated will be considered evaluable for response. These patients will have their response classified according to the definitions stated below. (Note: Patients who exhibit objective disease progression prior to the end of cycle 1 will also be considered evaluable.)

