5.3 Dose Expansion Cohorts

Once the RP2D is reached, an additional 15 patients will be treated at this dose. For the expansion cohort, patients will continue to be monitored for occurrence of DLT. Participants who go off-study during the 1st cycle of entinostat will be replaced in the escalation phase. Participants who do not complete the first 2 cycles of combined therapy without experiencing a DLT (as DLT period is defined in the first 2 combined therapy cycles) will also be replaced. To be DLT-evaluable, the patient must complete the first two cycles of combined therapy without experiencing a DLT. Any patient who is dose reduced during the entinostat run-in first cycle due to entinostat-related toxicity will be analyzed on the dose level that corresponds to the reduced dose level delivered during the first cycle of combined therapy.

The following early stopping rule for excess toxicity in the expansion cohort will be used: We will cease enrollment in the expansion phase at the dose determined from dose escalation part of the study if we observe two or more DLTs among the first six evaluable patients enrolled in the expansion cohort. An evaluable patient is any patient who received a study drug. If the true toxicity rate is 50% or greater at the MTD then this rule will stop the trial with probability at least .89. Similarly, if the true toxicity rate is 33% at the MTD then this stopping rule will end the trial with probability .65. In that event, a new expansion cohort will start at the dose level immediately below the dose level that was expanded. If the dose level being expanded is dose level -1, then the study will be terminated.

Monitoring of all safety and toxicity data is done by the Principal Investigator and the Corresponding Organization on a real-time basis as data are entered into Medidata Rave using the Web Reporting Module. All participating sites are expected to notify the Principal Investigator when a DLT has occurred.

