5.6 Duration of Follow Up

Patients will be followed closely throughout the study period and for 6 months after the last dose of entinostat in combination with pembrolizumab (MK-3475) or 6 months after they are removed for the presence of any toxicity (early or late).

During maintenance: Patients whose primary oncologist is at one of the study sites will be followed and seen by a member of the study team at least monthly in person or by phone when study visits are not required. For patients who are followed by an oncologist outside of one of the study sites, a study team member will evaluate the patients at least monthly in person or by phone.

During 6 months post last dose or after removal from study: all patients will be evaluated by the study team at least monthly. Evaluations may be done during routine clinic visits in patients followed longitudinally at the study Cancer Center or via phone if in person visits are not possible due to logistical reasons. The study team will note the follow-up in the medical records and source documents will be sought for any change in condition related to the study or study drug.

Patients removed from study for unacceptable adverse event(s) will be followed in person or by phone until resolution or stabilization of the adverse event OR for at least 6 months after removal from study. Prior data have showed a median OS of 5 months for patients with HR-MDS who

failed 5-AZA or Decitabine. Therefore, we expect to capture most events of progression, relapse or death during the maintenance and follow-up phases of the study. For patients who are still alive at end of follow-up period, we will check social security Death Index every 3 months for 2 more years to obtain death dates for OS calculations

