13.2 Sample Size/Accrual Rate

We expect to accrue 1-2 patients with MDS per month once the study is open.

Currently there is no therapy that has been shown to prolong survival in MDS in the post-DNMTi setting and that the expected best response in patients receiving supportive care only in post-DNMTi setting is negligible (1% or less). It is generally accepted that a $\geq 15\%$ ORR in the post-DNMTi is clinically meaningful and would be worth further evaluation in larger studies.

The total number of patients enrolled in the study will range from 21 to 27. The null hypothesis response rate of 1% (only supportive care) will be rejected if we observe 2 or more favorable responses. These criterion has significance level between .02 and .03 using a one-sided binomial test. This criterion has power between .84 and .93 for testing an alternative response rate of 15% with the combination therapy. Therefore, we will treat a total of 21 patients in the combination arm (6 in the first part of the study and 15 in the second part of the study).

DOMESTIC PLANNED ENROLLMENT REPORT						
Racial Categories	Ethnic Categories				Total	
	Not Hispanic or Latino		Hispanic or Latino			
	Female	Male	Female	Male		
American Indian/ Alaska Native	1	1	1	1	4	
Asian	1	1	0	0	2	
Native Hawaiian or Other Pacific Islander	1	0	0	0	1	
Black or African American	1	1	1	1	4	
White	4	4	1	1	10	
More Than One Race	0	0	0	0		
Total	8	7	3	3	21	

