13.5 Reporting and Exclusions

- 13.5.1 Evaluation of toxicity: All patients will be evaluable for toxicity from the time of their first treatment with entinostat/ Pembrolizumab (MK-3475).
- 13.5.2 Evaluation of response: All patients included in the study will be assessed for response to treatment, even if there are major protocol treatment deviations or if they are ineligible. Each patient will be assigned one of the following categories: 1) complete response, 2) partial response, 3) stable disease, 4) progressive disease, 5) early death from malignant disease, 6) early death from toxicity, 7) early death because of other cause, or 9) unknown (not assessable, insufficient data). [Note: By arbitrary convention, category 9 usually designates the “unknown” status of any type of data in a clinical database.]

All of the patients who met the eligibility criteria (with the possible exception of those who received no study medication) should be included in the main analysis of the response rate. Patients in response categories 4-9 should be considered to have a treatment failure (disease progression). Thus, an incorrect treatment schedule or drug administration does not result in exclusion from the analysis of the response rate. Precise definitions for categories 4-9 will be protocol specific.

All conclusions should be based on all eligible patients. Sub-analyses may then be performed on the basis of a subset of patients, excluding those for whom major protocol deviations have been identified (e.g., early death due to other reasons, early discontinuation of treatment, major protocol violations, etc.). However, these sub-analyses may not serve as the basis for drawing conclusions concerning treatment

efficacy, and the reasons for excluding patients from the analysis should be clearly reported. The 95% confidence intervals should also be provided.

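### Sections 11.1 and 13.5.2 give conflicting denominators for the response rate, and the 11.1 version drops early losses and biases the ORR upward

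*Combined protocol and SAP*

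**What the plan says.** Section 11.1 (Definitions) says that only patients who have measurable disease at baseline, "have received at least one cycle of therapy, and have had their disease re-evaluated will be considered evaluable for response". A note adds one exception: "Patients who exhibit objective disease progression prior to the end of cycle 1 will also be considered evaluable".

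Section 13.5.2 (Evaluation of response) takes the opposite approach. "All patients included in the study will be assessed for response to treatment, even if there are major protocol treatment deviations", and ineligible patients are assessed too. For the main response-rate analysis, "All of the patients who met the eligibility criteria (with the possible exception of those who received no study medication) should be included". Categories 4 to 9, which cover progression, early death from any cause and unknown status, count as treatment failure. Conclusions must rest on all eligible patients, and subset analyses may not support efficacy conclusions.

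Section 13.2 plans the test: "we will treat a total of 21 patients in the combination arm" (6 in part 1 and 15 in part 2). Total enrolment is 21 to 27. A 1% null rate is rejected with two or more responses, at a stated one-sided level of .02 to .03 and power of .84 to .93 against 15%.

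On replacement, Section 5.3 says of "Participants who do not complete the first 2 cycles of combined therapy without experiencing a DLT" that they will be replaced, and sets no limit to one phase. The synopsis (Part 2), Section 5.2 and Section 13.1 restrict the same rule to dose escalation. Patients who leave during the run-in cycle are replaced in the escalation phase only (synopsis, Section 5.3). No section says whether a replaced patient stays in the ORR.

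**The concern.** Sections 11.1 and 13.5.2 cannot both define the ORR denominator, and no text ranks them. They part company on patients lost early without a documented progression. None of these patients is a responder, so excluding them can only raise the estimate.

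This matters because efficacy is the only secondary objective (Section 1.2). The synopsis endpoint list and Section 13.1 both compare the ORR with a target of at least 15% for continuing. Early loss is also plausible in this population. Section 5.6 states: "Prior data have showed a median OS of 5 months for patients with HR-MDS" after failure of azacitidine or decitabine.

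The 11.1 rule is hard to apply in any case. Measurable disease is not a term in the modified IWG-2006 criteria reproduced in Appendices A1 and A2, and the protocol does not define it for MDS.

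**Working it through.** **1. The plan's own figures.** Section 13.2 gives the inputs: null 1%, alternative 15%, reject at two or more responses, N from 21 to 27. The formula is P(X ≥ 2) = 1 − (1 − p)^N − N·p·(1 − p)^(N − 1).

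- N = 21, p = .01: 1 − .8097 − .1718 = .0185. At p = .15 the power is .845.
- N = 27, p = .01: .0297. At p = .15 the power is .928.

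These agree with the stated ranges to rounding. The arithmetic is sound. What is unsettled is which patients make up N.

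**2. The two rules applied to the same eligible, treated patient.** The calendar in Section 10 puts a marrow at days 17 to 20 of cycle 1, so one cycle plus a re-evaluation is reached at about week 3.

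| Patient | Section 11.1 | Section 13.5.2 |
|---|---|---|
| Dies on day 15, no documented progression | Not evaluable | Failure |
| Withdraws on day 15, not re-evaluated | Not evaluable | Failure (unknown) |
| Progression documented on day 15 | Evaluable | Failure |
| Completes run-in and marrow, then leaves before pembrolizumab | Evaluable | Included |

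The sections differ in the first two rows. The last row shows that 11.1 can be met on entinostat alone, because pembrolizumab starts in cycle 2.

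**3. Size of the early loss.** Inputs are the 5-month median (Section 5.6), 30.44 days per month, and an assumed exponential shape. The proportion dead by day 21 is 1 − 2^(−21/(30.44 × median)).

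- Median 5 months: 1 − 2^(−21/152.2) = .091, and 21 × .091 = 1.9, or about 2 patients.
- Assumed range: a 4-month median gives .113 (2.4 of 21); a 12-month median gives .039 (0.8 of 21).

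**4. Effect on the ORR with three responders.**

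- All eligible patients: 3/21 = 14.3%.
- One early loss dropped: 3/20 = 15.0%.
- Two dropped: 3/19 = 15.8%.

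The expected inflation factor is 1/.909 = 1.10 at a 5-month median, and 1.04 to 1.13 for medians of 12 to 4 months.

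**5. Effect on the decision rule.** Rejection depends on the number of responses. Removing non-responders leaves that number as it was, so three responders pass on either denominator. Only the reported rate and its comparison with 15% move.

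**The case against.** The strongest reply is that 13.5.2 is the analysis section and already settles the matter: eligible patients "should be included in the main analysis of the response rate", early losses are failures, and subsets cannot support conclusions. If it is followed, the bias does not arise. That is right as far as it goes, and the remedy is simply to adopt that rule. But 11.1 is a current, explicit definition of who is evaluable for response, and an analyst who applies it gets a different ORR.

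It can also be said that the 9% is assumption-bound. The 5-month median is for higher-risk MDS, while Section 3.1.1 admits any IPSS risk. Patients whose progression is documented before an early death remain evaluable under 11.1. Withdrawals without re-evaluation would add to the loss, but the documents give no withdrawal rate. This stands, and it is why a range is shown.

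A reader might infer more than the documents support:

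- *That there are three incompatible denominators.* The 21 in Section 13.2 is a planning number, not an inclusion rule, and the same section allows 21 to 27 enrolled. The firm conflict is between two sections.
- *That the ORR becomes a rate among nine-week survivors.* The run-in plus two combined cycles is 63 days. Under the same 5-month assumption, 25% die by then, which would give 3/16 = 18.8%. But 11.1 conditions on about week 3. The nine-week version requires replaced patients to be dropped from the ORR, which no section says and 13.5.2 would forbid.
- *That replacement pushes type I error out of range.* Reaching 28 patients (21/.751) needs replacement in all 21 places, for which only the wording of Section 5.3 gives any support. Even then the error is .0318, which rounds to the stated .03. If only the six escalation places are refilled, 6/.751 is about 8, N is about 23, and the error is .022.
- *That progression in the run-in means automatic replacement.* The run-in replacement rule turns on going off-study. Sections 5.5 and 5.9 allow some clinically stable patients to continue treatment while progression is being confirmed.

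**Conclusion.** The conflict is real and two-way. Sections 11.1 and 13.5.2 disagree about patients lost before re-evaluation without documented progression, and the 11.1 version biases the ORR upward. The likely size is modest: about 1.5 percentage points in the three-responder example (15.8% against 14.3%). In a trial of 21 that is enough to move the estimate across the 15% target. This rests on exponential survival, the 5-month median, and those early deaths having no progression documented first. A longer median shrinks it. Part of the synopsis gives 20% as the goal instead, and both figures fall below that.

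The two-response test is not affected, and the stated error rates reproduce for N of 21 to 27. Two related gaps remain: whether replaced patients stay in the ORR, and the difference between Section 5.3 and the synopsis, Section 5.2 and Section 13.1 on where replacement applies.

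**What to change.** - Delete the response-evaluable definition in Section 11.1 and use 13.5.2 throughout. The main ORR then includes every eligible patient who received any study drug, with early death, withdrawal or absence of re-evaluation counted as non-response.
- State that patients replaced for DLT purposes remain in this denominator.
- Reconcile the replacement wording of Section 5.3 with the synopsis, Section 5.2 and Section 13.1.
- Report the ORR among patients who received pembrolizumab only as a labelled sub-analysis.
- Restate type I error and power at the N actually analysed (.0185 and .845 at 21; .0297 and .928 at 27).
- Since 13.5.2 would now govern, add hematologic improvement to its category list. The ORR counts it, but the list does not contain it.

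The cost is wording only. The headline ORR may be slightly lower than under 11.1.

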11.2 Response criteria

Myelodysplastic syndrome (MDS)

Responses for MDS patients will be defined as in the modified IWG-2006 criteria ([Appendix A1](#) and [Appendix A1](#)). These response criteria do not apply to AML as these patients are required to be in full remission by eligibility criteria. Only relapse and survival as measured by PFS and overall survival will be measured to assess response for AML patients. The OS and PFS will be measured for both AML and MDS as described in [Appendix A1](#) and [Appendix A2](#).

Duration of response: The duration of overall response is measured from the time measurement criteria are met for CR or PR (whichever is first recorded) until the first date that recurrent or progressive disease is objectively documented (taking as reference for progressive disease the smallest measurements recorded since the treatment started).

Duration of stable disease: Stable disease is measured from the start of the treatment until the criteria for progression are met.

Chronic Myelomonocytic Leukemia (CMML)

The definitions below are consistent with those detailed by Cheson, et al for MDS⁶¹ except that, as discussed earlier, for disease progression based on BM blast percentage, the patient must exceed 10% absolute BM blast percentage in addition to increasing above 50% of BM blast percentage at baseline to count as disease progression.

Complete response is defined by bone marrow showing <5% myeloblasts with normal trilineage maturation without dysplasia. When erythroid precursors constitute <50% of marrow cells, the blast percentage is based on total nucleated cells; otherwise, the blast percentage is based on non-erythroid compartment. Peripheral blood criteria consist of Hemoglobin \geq 11 gm/dl, ANC \geq 1 x 10⁹/L, Platelets \geq 100 x 10⁹/L, absence of peripheral blood blasts, all in the absence of transfusions and growth factors.

Partial response is defined by all of the above criteria with the exception of bone marrow blasts decreasing by >50% from pretreatment levels and/or achievement of a less advanced MDS FAB classification.

Stable Disease is defined by failure to achieve PR but without progression for at least 2 months.

Progression is defined according to initial blast percentages:

For patients with <5% blasts: \geq 50% increase in blasts to >10%

For patients with 5-10% blasts: \geq 50% increase in blasts to >10%

For patients with >10-20% blasts: \geq 50% increase in blasts to >20%

For patients with >20-30% blasts: \geq 50% increase in blasts to >30%

In addition, there must be \geq 1 of the following criteria: \geq 50% decrease from maximum response levels in granulocytes or platelets, a decrease in hemoglobin concentration by at least 2 gm/dl, or becoming transfusion dependent.

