3. PATIENT SELECTION

3.1 Eligibility Criteria

3.1.1 Pathologically confirmed MDS diagnosis (regardless of initial IPSS risk category) or oligoblastic AML with 21-30% BM blasts in whom DNMTi have failed. Patients who have developed AML after DNMTi therapy can be enrolled as long as they have initiated DNMTi therapy while they were in the MDS or oligoblastic AML (20-30% BM blasts) phase and the study chair agrees. Failure of DNMTis is defined as: Failure to achieve a CR, PR or HI after at least 4 cycles of DNMTi or progressed after such therapy.

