Assessment of response will occur after 4 combination cycles and similar to part 1, those who achieve an objective response or SD will continue to receive the therapy till progression. Patients who progress or respond and subsequently lose response will be withdrawn from study. BM biopsy/aspirate and PB samples will be done at baseline, after first cycle of ENT monotherapy, every 2 cycles of combined therapy, and at time of progression or study discontinuation. Formal safety assessment will be performed after the first 6 patients are enrolled and each have received at least 5 cycles (i.e. 1 ENT monotherapy cycle and 4 cycles of combined therapy (DL1, DL2) for each patient) to assess for any unexpected autoimmune or other toxicity.

Primary Endpoint(s): MTD will be defined by the occurrence of DLT among 2 dose schedules (see section 5.2)

Definitions of DLT: see section 5.2

The following early stopping rule for excess toxicity in the expansion cohort will be used: We will cease enrollment in the expansion phase at the dose determined from dose escalation part of the study if we observe two or more DLTs among the first six evaluable patients enrolled in the expansion cohort. An evaluable patient is any patient who received a study drug. If the true toxicity rate is 50% or greater at the MTD then this rule will stop the trial with probability at least .89. Similarly, if the true toxicity rate is 33% at the MTD then this stopping rule will end the trial with probability .65. In that event, a new expansion cohort will

start at the dose level immediately below the dose level that was expanded. If the dose level being expanded is dose level -1, then the study will be terminated.

Secondary Endpoint(s): Overall response rate (CR, PR, and HI) as defined by the modified International working group 2006 (IWG-2006) criteria for CR, PR, HI ([Appendix A1](#) and [Appendix A2](#)) with at least 15% to be continued

Exploratory Endpoint(s):

- Median response duration for responders, median time of progression to AML, median overall survival (OS) and 1- and 2-year OS rate
- Assessment of the dynamic quantitative change in proportion of MDSCs in BM with combined therapy (target of reducing to <10%) and correlation with any observed clinical responses

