13.4 Analysis of Secondary Endpoints

Overall response rate: defined by the International working group 2006 (IWG-2006) criteria for CR, PR, HI ([Appendix A1](#) and [Appendix A2](#)). We will also record PFS and OS for the

MDS. These endpoints will be assessed after cycle 2 and 4 of induction therapy, and every 3 months during follow-up. Bone marrow biopsies will be done at baseline, after 1 cycle and then every 2 cycles, at end of study, and as clinically indicated (e.g. suspicion of progression, decreasing blood counts). We aim to obtain preliminary efficacy data of entinostat in combination with Pembrolizumab (MK-3475) in terms of CR, PR, HI as defined by IWG-2006 and PFS, OS. Rates of CR, PR and HI will be summarized separately by cohort and reported with an exact 95% confidence interval. Median PFS and OS will also be reported with a 95% confidence interval.

The quantitative change in MDSCs (% MDSCs by flow cytometry, QIF score by AQUA) during treatment with the ENT/anti-PD1 combined therapy will be estimated using mixed effects models to take into account the within-patient correlation. Likelihood ratio tests will be performed to confirm if random intercepts and slopes are necessary in the model. The fixed effect for change in MDSCs over time will be evaluated for significance. The variability in the rate of change in MDSCs across patients will also be examined. The association between the clinical outcome and a meaningful reduction in MDSCs, which will be defined after a review of the data, will be assessed with the chi-square test. The quantity of MDSCs at baseline and during treatment as continuous variables can also be compared between responding and non-responding patients using a t-test or Mann-Whitney U-Test, if more appropriate.

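### Section 11.2 removes AML patients from response scoring because of a remission requirement that eligibility does not contain, and so contradicts sections 11 and 13.5.2

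*Combined protocol and SAP*

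**What the plan says.** All places are in the combined protocol and SAP.

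- **Section 11.2**, after pointing MDS patients to the modified IWG-2006 criteria, says: "These response criteria do not apply to AML as these patients are required to be in full remission by eligibility criteria". The next sentence reads: "Only relapse and survival as measured by PFS and overall survival will be measured to assess response for AML patients".
- **Section 3.1.1** (and the synopsis) admits "oligoblastic AML with 21-30% BM blasts in whom DNMTi have failed". It also admits patients whose AML developed after DNMTi therapy, provided "they have initiated DNMTi therapy while they were in the MDS or oligoblastic AML (20-30% BM blasts) phase and the study chair agrees". DNMTi failure means no CR, PR or HI after at least four cycles, or progression afterwards.
- **Section 11** says: "Responses in AML patients will be assessed using IWG 2003 criteria", and cites Appendix A3.
- **Section 13.1** gives the secondary endpoint as "Overall response rate (CR, PR, and HI) as defined by the modified International working group 2006 (IWG-2006) criteria". **Section 13.4** has the same definition: "Overall response rate: defined by the International working group 2006 (IWG-2006) criteria for CR, PR, HI". Both cite Appendices A1 and A2, and neither cites A3.
- **Section 13.2** tests a 1% null response rate, which "will be rejected if we observe 2 or more favorable responses", in 21 to 27 patients.
- **Section 13.5.2** has all patients assessed for response, gives each a category that may be CR or PR, and keeps all eligible patients in the main analysis.

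**The concern.** The reason that section 11.2 gives for setting AML patients apart is not true of the population the protocol enrols. An AML patient in this trial enters with active disease after failed treatment. Such a patient has no remission from which to relapse, so measuring relapse in place of response leaves nothing to score at the start.

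The consequence falls on the response test. Its threshold is two responses, so the handling of a single patient can decide it. Under section 11.2 an AML patient who responds adds nothing to the count, although section 13.5.2 keeps that patient in the analysis. Under section 11 the same patient can be a responder. In an open-label, single-arm study the rule should be fixed before responses are known.

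**Working it through.** **Step 1. Is there a remission requirement?** Sections 3.1 and 3.2 contain none. The AML routes into the trial are 21-30% marrow blasts with DNMTi failure, and AML that arose after DNMTi. Post-transplant patients (section 3.1.8) must have relapsed. Eligibility therefore points to active disease.

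**Step 2. What do the other sections do with AML patients?**

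| Place | AML patients |
|---|---|
| Section 11 | Response scored by IWG 2003 (Appendix A3) |
| Section 11.2 | IWG-2006 does not apply; relapse, PFS and OS only |
| Section 13.5.2 | Assessed for response like everyone else |
| Sections 13.1, 13.4 | General ORR definition by IWG-2006; silent on AML |

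The first half of section 11.2, that the IWG-2006 criteria do not apply to AML, agrees with section 11. The conflict lies in the remission reason and in the sentence that follows it.

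**Step 3. Reproduce the plan's figures.** Inputs from section 13.2: null rate .01, alternative .15, reject at X ≥ 2, n from 21 to 27. The formula is P(X ≥ 2) = 1 − (1−p)^n − n·p·(1−p)^(n−1).

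- n = 21, p = .01: 1 − .8097 − .1718 = .0185. With p = .15: 1 − .0329 − .1221 = .845.
- n = 27: alpha .0297, power .928.

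The plan states .02 to .03 and .84 to .93. These reproduce at the two decimals printed, and no stated figure is disputed.

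**Step 4. Can one AML patient decide the test?** Take 21 patients, one MDS responder and one AML responder.

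- Section 11.2: one response. P(X ≥ 1 | 21, .01) = 1 − .99^21 = .190, so the null is kept.
- Section 11, if the AML response counts toward ORR: two responses. P(X ≥ 2 | 21, .01) = .0185, so the null is rejected.

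The observed rates are 1/21 = 4.8% and 2/21 = 9.5%. Both are below the 15% target in section 13.1.

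**Step 5. Power, as an illustration.** Let k be the number of AML patients who cannot be scored. The documents do not give k, so the values below are assumptions; they also assume the 15% rate in every patient who can be scored. Power is then P(X ≥ 2 | n − k, .15). It is the same whether the k patients are dropped or kept as non-responders, because the rule depends on the count alone.

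| k | n = 21 |
|---|---|
| 0 | .845 |
| 1 | .824 |
| 3 | .776 |
| 5 | .716 |

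At n = 27, power is .928 with k = 0. It is still .845 with k = 6, since 27 − 6 = 21.

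**Step 6. Does deleting the section 11.2 text settle everything?** Not quite. Section 13 does not say how an Appendix A3 response enters the ORR. A3's complete and partial remission rows correspond to CR and PR. The leukemia-free-state row has no stated place in ORR, and A3 as reproduced has no HI row (the table is damaged in the text available, so its detail should be read with care). Patients with 21-30% blasts could be read under either set: section 3.1.1 calls them oligoblastic AML, Appendix B says they may be considered MDS or AML, and Appendix A1 has a progression row for 20%-30% blasts.

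**The case against.** The best defence is that section 11.2 carries a leftover sentence that no one would follow. Its reason is false for every eligible patient, section 11 gives a specific AML rule, and section 13.5.2 has all patients assessed for response with CR and PR open to them. Two sections thus place AML patients in the numerator as well as the denominator. That is a fair reading, and probably the intended one. It does not remove the problem: the sentence is current text in the section that defines response, it states a rule rather than a remark, and ignoring it still leaves the Appendix A3 question in section 13 unanswered.

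Three stronger readings are tempting, and the documents do not support them.

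- A reader might infer three competing rules for AML. Sections 13.1 and 13.4 give a general ORR definition that omits a cross-reference to A3. They are not a rival AML rule.
- A reader might infer that the continuation decision turns on this. In the worked example both rates miss the 15% target, so only rejection of the 1% null changes.
- A reader might infer that the trial is underpowered. No AML share is given, and section 13.2 speaks of accruing patients with MDS. The fall below .84 at n = 21 with one unscorable patient is from .845 to .824, and it depends on an assumed count.

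**Conclusion.** The point stands and should be corrected, at modest weight. Section 11.2 states a remission requirement that eligibility does not contain, and rests on it a restriction that contradicts sections 11 and 13.5.2. Followed literally, it bars AML patients from counting as responders, and one such patient can decide rejection of the 1% null (p = .19 against p = .0185 in 21 patients).

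The limits are plain. ORR is a secondary endpoint, the MTD is not touched, and the plan's own alpha and power are correct for its rule. The worked example assumes exactly one MDS and one AML responder, and that an Appendix A3 response counts toward ORR. The power figures are illustrations and should carry no weight in judging severity.

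**What to change.** - In section 11.2, delete the sentence on full remission and the following sentence that restricts AML to relapse and survival.
- In sections 13.1 and 13.4, carry over section 11's rule that AML patients are scored by Appendix A3.
- State, before any response analysis, which A3 categories count toward ORR. Complete and partial remission map to CR and PR; decide on leukemia-free state, and on whether HI can be credited to an AML patient.
- Name one criteria set for patients with 21-30% blasts.
- Report MDS and AML responses separately beside the combined rate.

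The cost is a wording amendment to three sections. Sample size, decision rule and treatment do not change. The drawback is that the combined ORR will mix two sets of response criteria, which is the reason for showing the two groups separately.
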